15. STUDY LIMITATIONS

[figure not shown]
SMS alone cannot directly improve the health care system or address the third delay in care (delay in receiving quality care). There are many other external factors – partner, socioeconomic factors, quality of facility-based care – that may not be modulated by SMS messaging. This may limit our ability to detect an impact on the primary outcome of neonatal mortality. Evaluation of the impact of SMS on secondary outcomes of ENC, knowledge of warning signs, care seeking and maternal mental health will nonetheless enable us to assess whether the SMS intervention has the desired impact and has potential to improve mortality in combination with additional health systems strengthening. Moreover, these **secondary outcomes have value in improving neonatal and maternal health in their own right**. Fidelity and generalizability of dialogue interventions are challenging. We have extensive experience in standardizing messaging dialogue, but it will not be possible to completely standardize the nurse responses in the intervention. This challenge however is part of routine medical care and any type of behavioral interventions involving health workers. Implementation and evaluation in four sites will increase the generalizability of any measured effect. With regards to the care seeking outcome, babies in the control arm may have higher numbers of clinic visits and/ or hospitalizations if their mothers are less likely to practice ENC or if mothers seek care later in the illness process. If we observe this effect we will compare illness severity at presentation between the two arms using a validated neonatal illness assessment. Women in the trial cannot be blinded to their assignment, which may lead to performance bias. Additionally, outcomes obtained by self-report could introduce bias for social desirability, but this will likely occur across all arms.

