## 2. STUDY ENDPOINTS

Primary study endpoints:

1. **Neonatal mortality** will be defined as death of a live-born infant within 28 days of birth, based on mother's report, verbal autopsy, or clinic records.

Secondary endpoints:

1. **Early neonatal mortality** will be defined as death of a live-born infant within 7 days of birth, based on mother's report, verbal autopsy, or clinic records.
2. **Initiation of early breastfeeding** will be defined as initiation of breastfeeding within the first hour of life, based on maternal self-report at 2-week postpartum study visit.
3. **Cessation of exclusive breastfeeding** in the first 6 weeks of life will be ascertained based on maternal self-report at the 2-week and 6-week visits.
4. **Bath** in the first 24 hours of life will be ascertained based on maternal self-report at the 2-week visit.
5. **Application of substances to cord** will be ascertained based on maternal self-report at the 2-week visit.
6. **Maternal provision of Kangaroo Mother Care (KMC)** will be defined as proportion of mothers with low birth-weight or preterm babies (<2500g or <37 weeks EGA at birth) who report the baby spent any time skin-to-skin with an adult on  $\geq 10$  of the first 14 days at home.
7. **Maternal knowledge of neonatal danger signs** will be defined as the number of the 8 neonatal danger signs correctly named at 2-week and 6-week visits.
8. **Appropriate care seeking** will be defined as the proportion of illness episodes with danger signs where the infant attended the clinic and/or where the infant was hospitalized independent of neonatal danger signs in the first 18 weeks of life (study follow-up period). Illness episodes are based on maternal self-report and only include the most recent illness episode reported at the 6-week visit or 2-week visit if 6-week data is unavailable.
9. **Elevated depressive symptoms** will be defined as a score  $\geq 13$  on the Edinburgh Postnatal Depression Scale (range 0-30) at 2-week and 6-week visits.
10. **Social support score** will be defined by MOS social support score (range 0-100) at 2-week and 6-week visits.
11. **Self-efficacy** will be defined by the Karitane Parenting Confidence Scale score (range 0-45) at 2-week and 6-week study visits.

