### 5.3 Analysis of study endpoints

1. **Neonatal mortality.** Among live-born infants, the proportion who die in the first 28 days postpartum will be compared between arms by log-binomial regression. As a *secondary analysis* of this outcome, a Bayesian analysis will be conducted using Markov Chain Monte Carlo modeling to estimate the probability that the Mobile WACh NEO treatment effect exceeds a range of potential values. Models with a range of prior probabilities will be developed.
2. **Early neonatal mortality.** Among live-born infants, the proportion who die in the first 7 days postpartum will be compared between arms by log-binomial regression.
3. **Initiation of early breastfeeding.** Proportion of infants who initiate breastfeeding in the first hour of life will be compared between arms by log-binomial regression.
4. **Cessation of exclusive breastfeeding.** Time to first introduction of complementary foods will be compared between arms by Cox proportional hazards regression.
5. **Bath.** Proportion of infants who are bathed in the first 24 hours of life will be compared between arms by log-binomial regression.
6. **Application of substances to cord.** Proportion of infants who have any substance applied to their cord will be compared between arms by log-binomial regression.
7. **Maternal provision of Kangaroo Mother Care (KMC).** Among women whose babies were born at <37 weeks gestation or weighing <2500g, proportion of who provide KMC on  $\geq 10$  of the first 14 days that the baby is home will be compared by log-binomial regression.
8. **Maternal knowledge of neonatal danger signs.** The mean number of 8 neonatal danger signs correctly named by mothers at the 2-week and 6-week visits will be compared between arms by Poisson generalized estimating equations (GEE). Exploratory analyses will evaluate time-dependent effects by incorporating timepoint as an interaction term.
9. **Appropriate care seeking.** The proportion of illness episodes with danger signs where the infant attended the clinic and/or where the infant was hospitalized independent of neonatal danger signs in the first 18 weeks of life (study follow-up period). Illness episodes are based on maternal self-report and only include the most recent illness episode at the 6-week visit, or 2-week visit if data is unavailable at the 6-week visit. Differences in proportions will be compared between arms by log-binomial regression.

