**Table 5.2 Summary of statistical analyses**

Outcome	Indicator	Timing	Statistical Analysis
Primary outcome			
Neonatal mortality	Death during 1 st 28 days of life	2 and 6 week visits, clinic record abstraction	Log-binomial regression
Secondary outcomes			
Early neonatal mortality	Death during 1 st 7 days of life	2 and 6 week visits, clinic record abstraction	Log-binomial regression
Initiation of early breastfeeding	Breastfeeding in 1 st hour of life	2 week visit	Log-binomial regression
Exclusive breastfeeding	Cessation of EBF in 1 st 6 weeks of life	2 and 6 week visits	Cox proportional hazards
Thermal care	Bath in 1 st 24 hours of life	2 week visit	Log-binomial regression
Cord care	No application of substances to cord	2 week visit	Log-binomial regression
Home provision of KMC	Any duration of skin-to-skin care on ≥10 of the first 14 days at home, among low birthweight or preterm infants	2 and 6 week visits	Log-binomial regression
Maternal knowledge of neonatal danger signs	Number of the 8 danger signs or symptoms successfully named	2 and 6 week visits	Poisson GEE
Appropriate care seeking	Proportion of illness episodes with danger signs where the infant attended the clinic and/or where the infant was hospitalized regardless of danger signs reported in study follow-up	2 and 6 week visits, ongoing record abstraction	Log-binomial regression
Depression	Score above diagnostic threshold (≥13) for Edinburgh Postnatal Depression Scale	Baseline, 2 and 6 week visits	Log-binomial GEE
Social support	Score using MOS Social Support Survey	Enrollment, 2 and 6 week visits	Linear GEE
Self-efficacy	Score using Self-efficacy in Infant Care Scale	Baseline, 2 and 6 week visits	Linear GEE

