**Table 5.3 Study endpoints: shell table**

	Overall	Control	SMS	p-value
Aim 1				
* Neonatal mortality (per 1000 live births)				
Aim 2				
* Early neonatal mortality (per 1000 live births)				
\$ Time to introduction of complementary food				
* Breastfeeding initiated within 1 hour (%)				
* Bathed within 24 hours (%)				
* Substances applied to cord (%)				
* Provision of KMC among LBW/PTB infants (%)				
^ Number of danger signs identified				
+ Proportion of illness episodes with danger signs or hospitalization				
Aim 3				
+ Elevated depressive symptoms (%)				

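### The care-seeking proportion counts admissions without danger signs as successes although its stated base is danger-sign episodes, so it moves with admissions as well as with care seeking

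*SAP*

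**What the plan says.** SAP section 5.3 item 9 gives this rule: "The proportion of illness episodes with danger signs where the infant attended the clinic and/or where the infant was hospitalized independent of neonatal danger signs". The window is follow-up of up to 18 weeks. Section 2 (secondary endpoint 8) has the same rule. Table 2.1 and Table 5.2 restate it, Table 5.2 with the wording "where the infant was hospitalized regardless of danger signs reported in study follow-up". The episodes counted "only include the most recent illness episode at the 6-week visit, or 2-week visit if data is unavailable at the 6-week visit", so there is at most one per visit history. On the model, section 5.3 says: "Differences in proportions will be compared between arms by log-binomial regression".

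None of these places says where a hospitalised episode without danger signs sits in the denominator. The only hint is the row label in the Table 5.3 shell: "Proportion of illness episodes with danger signs or hospitalization". That row also carries the mark for log-binomial GEE, whereas section 5.3, Table 5.2 and the April 2023 entry in Table 6.1 all give log-binomial regression.

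The protocol (Table 4) defined the outcome as a count of danger-sign clinic visits and/or hospital admissions, analysed by Poisson regression. SAP Table 6.1 records the change to a proportion, made because care seeking had been collected only for the most recent episode.

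**The concern.** In a count per infant, adding admissions needs no denominator. In a proportion it does. The hospitalisation term was kept when the outcome changed, and no base was stated for it.

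Two analysts could therefore follow the SAP and report different numbers. On the base suggested by Table 5.3, inclusion depends on the outcome: an infant without a reported danger sign is counted if admitted and ignored if not.

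This matters for interpretation because Protocol section 15 warns that "babies in the control arm may have higher numbers of clinic visits and/ or hospitalizations if their mothers are less likely to practice ENC". If such admissions are commoner among controls relative to danger-sign episodes, they raise the control arm's care-seeking figure, and illness prevented in the SMS arm would count against it on this Aim 2b endpoint.

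**Working it through.** **The plan's own figure.** The only power statement for care seeking (SAP section 3c) is at least 80% power for 0.50 vs 0.61 mean clinic visits at two-sided alpha 0.0045, with 2,500 per arm and 10% attrition. With 2,250 evaluable per arm and an assumed SD of 1 (none is stated), power is 80.2%, so the figure reproduces. It refers to a mean count; the proportion has no power calculation.

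**The candidate bases.** Let D be danger-sign episodes, c the share of D with care sought, H hospitalised episodes without danger signs, and M other episodes without danger signs.

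1. Base D, as written: (cD + H)/D. H lies outside the base, so there is no 0/1 record to model. The value passes 1 only if H > (1 − c)D. With D = 200 and H = 40 it is 0.80 at c = 0.60 and 1.15 at c = 0.95.
2. Base D + H (the union, Table 5.3 label): (cD + H)/(D + H) = c + (1 − c)·H/(D + H). It can be fitted, but it exceeds c whenever H > 0 and c < 1, by an amount set by H/D.
3. Base D + H + M (all most-recent episodes): (cD + H)/(D + H + M). It can be fitted, but it scores mild illness without danger signs as failure and still rises with H.
4. Base D with success confined to D: the value is c, whatever H is.

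**Size on the union base.** The documents do not give D, c or H, so the rates below are assumptions. D is a percentage of 2,250 infants per arm; H is a percentage of infants without a danger-sign episode. Worked example for the first row:

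- D = 0.15 × 2,250 = 337.5 in each arm, and care sought = 0.60 × 337.5 = 202.5.
- Control H = 0.02 × 1,912.5 = 38.25; SMS H = 0.01 × 1,912.5 = 19.125.
- Control: (202.5 + 38.25)/(337.5 + 38.25) = 0.641. SMS: (202.5 + 19.125)/(337.5 + 19.125) = 0.621. Ratio 0.97.

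Rejection rates come from 40,000 simulated trials per setting, using a two-sided Wald test of the log risk ratio at nominal 0.05.

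| D, control / SMS | Care sought | H, control / SMS | Union values | RR | Rejections |
|---|---|---|---|---|---|
| 15% / 15% | 60% / 60% | 2% / 1% | 0.641 / 0.621 | 0.97 | about 8% |
| 15% / 15% | 60% / 60% | 3% / 1.5% | 0.658 / 0.631 | 0.96 | 11–12% |
| 20% / 15% | 60% / 60% | 2% / 1% | 0.630 / 0.621 | 0.99 | 5.5% |
| 30% / 15% | 60% / 60% | 2% / 1% | 0.618 / 0.621 | 1.01 | about 5% |
| 15% / 15% | 60% / 60% | 2% / 2% | 0.641 / 0.641 | 1.00 | about 5% |
| 15% / 15% | 60% / 72% | 2% / 1% | 0.641 / 0.735 | 1.15 | 79% |
| 15% / 15% | 60% / 72% | 3% / 3% | 0.658 / 0.761 | 1.16 | 89% |

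Restricted to danger-sign episodes, the five null settings give RR 1.00 and about 5% rejections. The two settings with a true effect give RR 1.20 and 91% power. At the SAP's planning alpha of 0.0045, the sixth row has 46% power, against 66–67% on the danger-sign base.

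**The case against.** The strongest reply is that this is an unstated denominator and no more. The sentence can also be parsed with all most-recent illness episodes as the base, a success being a danger-sign episode taken to clinic or any admission. The numerator then lies inside the base and the model fits. That reading is possible, so the union is not the only base that can be fitted. But the definitions and Table 6.1 favour a danger-sign base, and the all-episode reading scores mild illness as a failure of appropriate care seeking.

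Second, the null bias depends on assumed inputs. Poorer newborn care would plausibly raise danger-sign episodes as well as admissions, and rows three and four of the table show the bias nearly gone in that case. This stands. The nominal 5% level is also not the trial's decision rule, since secondary outcomes are Benjamini-Hochberg adjusted.

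Third, Protocol section 15 goes on to plan a comparison of illness severity between arms if control admissions are higher. That is a real safeguard, but it is conditional and is not carried into the SAP.

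Three stronger readings are tempting. A reader might infer that the endpoint tracks admissions in place of care seeking; it does not, since a true ratio of 1.20 still shows as about 1.15. A reader might infer that the reported proportion will exceed 100%; that needs H > (1 − c)D on a base that could not be modelled anyway. A reader might infer a definite bias against the SMS arm; the direction depends on H/D in each arm, which the documents do not give.

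**Conclusion.** The concern holds as a defect of definition. The success rule reaches outside the stated base, and on the base that the shell table suggests, episodes without danger signs enter only as successes. The endpoint then mixes care seeking with admission frequency.

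The size is modest and uncertain. Under no effect the ratio runs from about 0.96 to 1.01 across the assumed settings, with rejections from about 5% to 12% at nominal 5%. A true ratio of 1.20 becomes about 1.15 to 1.16, so the dilution occurs even with equal admissions. All of this rests on assumed rates of danger-sign episodes, care sought and admissions. The mismatch between numerator and base rests only on the SAP's text. It affects one secondary endpoint and leaves the mortality analysis untouched.

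**What to change.** In SAP section 2 item 8, section 5.3 item 9 and Tables 2.1, 5.2 and 5.3:

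- Denominator: the most recent reported illness episode (6-week visit, else 2-week visit) with at least one danger sign.
- Success: clinic attended or infant hospitalised for that reported episode.
- Delete the clause that counts admissions irrespective of danger signs.
- Report hospitalisation for any reason as a separate row, by arm, among live-born infants.
- The documents do not show that admissions from record abstraction can be linked to a reported episode. Where they cannot, use the questionnaire report for that episode.
- Reword the Table 5.3 row to match and change its mark from log-binomial GEE to log-binomial regression.

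The cost is revised wording, one recoded variable and one extra table row, using the data held on the most recent episode. The downsides are slightly fewer episodes, no credit for admissions without a reported danger sign, and one more late change to log in Table 6.1 for an endpoint already redefined in December 2022 and April 2023.

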11.7 Data Analysis

Table 4: RCT outcomes

Outcome	Role	Indicator	Source	Timing of ascertainment	Statistical Analysis
Aim 1					
Neonatal mortality	Primary outcome	Death during 1 st 28 days of life	Questionnaire, clinic records; verbal autopsy	2 and 6 week visits, ongoing record abstraction	Cox proportional hazards
Aim 2					
Initiation of early breastfeeding	Secondary outcome	Breastfeeding in 1 st hour of life	Questionnaire	2 week visit	Poisson regression (robust standard errors)
Exclusive breastfeeding	Secondary outcome	Cessation of EBF in 1 st 6 weeks of life	Questionnaire	2 and 6 week visits	Cox proportional hazards
Thermal care	Secondary outcome	Bath in 1 st 24 hours of life	Questionnaire	2 week visit	Poisson regression (robust standard errors)
Cord care	Secondary outcome	No application of substances to cord	Questionnaire	2 week visit	Poisson regression (robust standard errors)
Maternal knowledge of neonatal danger signs	Secondary outcome	Number of the 7 danger signs or symptoms successfully named	Questionnaire	2 and 6 week visits	Poisson GEE
Appropriate care seeking	Secondary outcome	Number of clinic visits with danger sign and/or hospital admissions reported in 1 st 6 weeks	Questionnaire, clinic records	2 and 6 week visits, ongoing record abstraction	Poisson regression
Aim 3					

Depression	Secondary outcome	Score above diagnostic threshold (≥ 12) for Edinburgh Postnatal Depression Scale (70)	Questionnaire	Enrolment, 2 and 6 week visits	Poisson regression (robust standard errors)
Social support	Secondary outcome	Score using MOS Social Support Survey (71)	Questionnaire	Enrolment, 2 and 6 week visits	Linear GEE
Self-efficacy	Secondary outcome	Score using Self-efficacy in Infant Care Scale (68)	Questionnaire	Enrolment, 2 and 6 week visits	Linear GEE

For IDI analysis, two analysts will independently code transcripts to identify themes and sub-themes, coordinating analyses to create a comprehensive codebook and concept map. We will use domains identified under the IMB theory and our conceptual model to categorize participants' perceived intervention functions.

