**Table 2.1 Summary of primary and secondary endpoints**

Outcome	Indicator	Source	Timing
Primary outcome			
Neonatal mortality	Death during 1 st 28 days of life	Questionnaire, clinic records; verbal autopsy	2 and 6 week visits, clinic record abstraction
Secondary outcomes			
Early neonatal mortality	Death during 1 st 7 days of life	Questionnaire, clinic records; verbal autopsy	2 and 6 week visits, clinic record abstraction
Initiation of early breastfeeding	Breastfeeding in 1 st hour of life	Questionnaire	2 week visit
Exclusive breastfeeding	Cessation of EBF in 1 st 6 weeks of life	Questionnaire	2 and 6 week visits
Thermal care	Bath in 1 st 24 hours of life	Questionnaire	2 week visit
Home provision of KMC	Any duration of skin-to-skin care on $\geq 10$ of the first 14 days at home, among low birthweight or preterm infants	Questionnaire	2 week visit

Cord care	No application of substances to cord	Questionnaire	2 week visit
Maternal knowledge of neonatal danger signs	Number of the 8 danger signs or symptoms successfully named	Questionnaire	2 and 6 week visits
Appropriate care seeking	Proportion of illness episodes with danger signs where the infant attended the clinic and/ or where the infant was hospitalized regardless of danger signs reported during study follow-up	Questionnaire, clinic records	2 and 6 week visits, ongoing record abstraction
Depression	Score above diagnostic threshold ( $\geq 13$ ) for Edinburgh Postnatal Depression Scale	Questionnaire	Baseline, 2 and 6 week visits
Social support	Score using MOS Social Support Survey	Questionnaire	Enrollment, 2 and 6 week visits
Self-efficacy	Score using Karitane Parenting Confidence Scale	Questionnaire	Baseline, 2 and 6 week visits

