#### c. Analyses based on continuous variables

Assuming alpha=0.0045 (Bonferroni-adjusted for 11 tests), 2-sided test, 1:1 allocation ratio, with a sample size of 2,500 per arm, and 10% attrition, we will have  $\geq 80\%$  power to detect a difference in continuous scores of 0.11: 0.50 vs. 0.61 mean clinic visits, 3.00 vs. 3.11 mean danger signs named, and 2.50 vs. 2.61 mean social support score.

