## **4. USE OF INTENTION-TO-TREAT AND PER-PROTOCOL ANALYSES**

Analysis of primary outcomes will be by intention to treat (all participants).

After enrollment had begun, the study team became aware of other SMS health messaging interventions operating in the study area. On Aug 23, 2021, questions were added to the study visit questionnaire to ask participants if they were receiving SMS health messages from programs other than the Mobile WACh NEO study. Because the study was intended to evaluate the impact of the SMS program without contamination, the primary intention to treat analysis will be adjusted by whether participants ever reported receiving maternal health related SMS messages from other programs. Secondary sensitivity analysis will use per-protocol analysis, excluding participants who reported receiving SMS messages from other programs and excluding intervention participants who never successfully received any SMS from the study.

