**Figure 5.1 – Trial profile**

## 5.2 Baseline Characteristics

We will describe the distribution of baseline characteristics, using summary statistics appropriate for the measurement scale. We will present these summary statistics in tables both pooled and by study arm (see Table 5.2). To determine if the randomization resulted in balanced groups, baseline characteristics will be compared between randomization groups using Chi-square tests for categorical variables and the Kruskal-Wallis test for continuous variables. Any variables found to vary significantly at baseline will be included as adjustments in the primary analysis.

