10. **Elevated depressive symptoms.** The proportion of mothers with score  $\geq 13$  on the Edinburgh Postnatal Depression Scale at the 2-week and 6-week visits will be compared between arms by log-binomial GEE. Exploratory analyses will evaluate time-dependent effects by incorporating timepoint as an interaction term.
11. **Social support score.** The transformed mean social support score (range 0-100) at the 2-week and 6-week visits will be compared between arms using linear GEE. Exploratory analyses will evaluate time-dependent effects by incorporating timepoint as an interaction term.
12. **Self-efficacy.** The summed parenting confidence score (0-45) at the 2-week and 6-week visit will be compared between arms using linear GEE. Exploratory analyses will evaluate time-dependent effects by incorporating timepoint as an interaction term.

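### The SAP 5.2 adjustment rule can bring depression, social support and parenting confidence scores into the primary analysis, although the protocol reads as recording enrolment scores after the arm is known (minor)

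*SAP*

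**What the plan says.** **Timing of the enrolment questionnaire.** Protocol 11.6.i (Data collection) has staff administer it once a woman has been enrolled and randomized. Depression and social support are among its listed contents. Self-efficacy is not named there, but the list is introduced as partial. Protocol 11.6.i (Randomization) says that neither participants nor staff are blinded and that the program shows staff the allocation.

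**Schedule of the scores.** Protocol Table 4 gives the timing of all three Aim 3 outcomes as "Enrolment, 2 and 6 week visits". SAP Table 2.1 gives social support as "Enrollment, 2 and 6 week visits", and SAP Table 5.2 gives depression and self-efficacy as "Baseline, 2 and 6 week visits".

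**Aim 3 analysis.** SAP section 2 says that social support "will be defined by MOS social support score (range 0-100) at 2-week and 6-week visits". SAP 5.3 item 11 follows suit: "The transformed mean social support score (range 0-100) at the 2-week and 6-week visits will be compared between arms using linear GEE". Items 10 and 12 treat depression and self-efficacy in the same way. None of the three names a covariate.

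**Adjustment.** SAP Table 5.1 lists elevated depressive symptoms, social support and parenting confidence as baseline rows. SAP 5.2 compares baseline rows between arms by chi-square or Kruskal-Wallis test, at no stated level, and then says: "Any variables found to vary significantly at baseline will be included as adjustments in the primary analysis". SAP section 4 separately says that "the primary intention to treat analysis will be adjusted by whether participants ever reported receiving" messages from other programs.

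**The concern.** A baseline covariate is safe to adjust for because allocation cannot have affected it. A self-reported mood or support score taken after a woman has learned that she will, or will not, receive SMS support does not carry that guarantee. If knowing the arm changed the answers, the baseline test would tend to detect the change, and SAP 5.2 would then remove part of an effect of allocation from the model.

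The reach of the rule is also unclear. The primary analysis in SAP 5.2 could mean the mortality model alone or the main model for each outcome. In the first case the mortality risk ratio is exposed. In the second, so are the Aim 3 comparisons, where the enrolment score would be a strong predictor of the outcome.

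**Working it through.** **Inputs from the documents.** 2,500 women per arm, 10% attrition (2,250 evaluable), two-sided alpha 0.0045 for secondary outcomes, 80% power (SAP 3c); neonatal mortality of 23.0 and 12.2 per 1000 (SAP Table 3.1).

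**Assumptions, none of them in the documents.** SD of 1; a 5% level for the baseline tests; a shift at enrolment of 0.05 to 0.10 SD; correlation r of 0.3 to 0.6 between enrolment and follow-up scores; between-visit correlation rho of 0.5 to 0.7; a mortality risk ratio of 1.0 to 1.3 per SD of the score.

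**1. The SAP's own figure.** SAP 3c plans for a "difference in continuous scores of 0.11". For one follow-up value and no covariate, (2.841 + 0.842) × √(2/2250) = 0.1098. It reproduces, so the plan does not rely on baseline adjustment.

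**2. The planned two-visit GEE.** Multiply by √((1 + rho)/2):
- rho 0.5: 0.0951 SD
- rho 0.7: 0.1012 SD

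Both are smaller than 0.11, so no stated target is missed.

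**3. Chance of triggering the rule with no shift.** For three independent scores, 1 − 0.95³ = 14.3%. If the scores are correlated, it falls to about 11% at a pairwise correlation of 0.7. Adjusting for a purely chance imbalance does not bias the comparison.

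**4. Chance of triggering it with a shift.** For a continuous score with 2,500 per arm and a Kruskal-Wallis efficiency of 0.955, the expected z is shift × √(2500/2) × √0.955.
- 0.05 SD: z = 1.73, flagged 41%
- 0.10 SD: z = 3.46, flagged 93%

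For depression as a yes/no item at 19% prevalence (chi-square), the corresponding rates are 23% and 67% for a downward shift, and 23% and 70% for an upward one.

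**5. Effect on mortality if a shifted score enters.** Expected deaths are 2,250 × 0.023 = 51.75 and 2,250 × 0.0122 = 27.45. The SE of the log risk ratio is √(1/51.75 − 1/2250 + 1/27.45 − 1/2250) = 0.234. The largest movement considered is ln(1.3) × 0.10 = 0.026, which is 2.7% of the risk ratio and 0.026/0.234 = 0.11 SE.

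**6. Effect on an adjusted Aim 3 model.** The estimate moves by r × shift: from 0.3 × 0.05 = 0.015 SD to 0.6 × 0.10 = 0.060 SD. Against the 0.095 to 0.101 SD of step 2, the upper end is not trivial.

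**7. What adjustment would gain if the scores came before allocation.** Replace the factor in step 2 by √((1 + rho)/2 − r²).

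| rho | r | Detectable difference (SD) | Variance reduction |
|---|---|---|---|
| 0.5 | 0.3 | 0.0892 | 12.0% |
| 0.5 | 0.6 | 0.0686 | 48.0% |
| 0.7 | 0.3 | 0.0957 | 10.6% |
| 0.7 | 0.6 | 0.0769 | 42.4% |

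**The case against.** The best defence is that the Aim 3 analysis is fully specified. SAP section 2 and items 10 to 12 fix the outcome as the 2- and 6-week values. The column that lists baseline or enrolment is headed as timing and shows when data are collected, not which rows enter the model. That stands. A reader might infer from Table 5.2 that the GEE is incomplete, invalid or underpowered without the enrolment score. The documents do not support this: the unadjusted two-visit comparison is valid, and it does better than the planned 0.11. Leaving out the covariate is a choice that costs only precision, and that precision can safely be recovered in the main result only if the scores preceded allocation, contrary to how Protocol 11.6.i reads.

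A reader might also infer that knowledge of the arm distorted the enrolment answers, or that the mortality result is biased. Nothing in the documents shows a shift. The 41% to 93% depends on shifts assumed here, and even the largest of them moves the mortality estimate by about a tenth of its standard error.

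Third, the timing rests on one sentence, which may describe the visit loosely, and for self-efficacy it is an inference from the enrolment timing in Protocol Table 4. That is fair, and is why the SAP should state the order.

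What the defence does not answer is that, as written, a post-allocation score can trigger adjustment of the primary analysis. No entry in SAP Table 6.1 removes that.

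**Conclusion.** The point holds and is minor. Read together, Protocol 11.6.i, SAP Table 5.1 and SAP 5.2 allow adjustment for a score recorded after the arm was known, and SAP 5.2 does not say which models it governs. The passages establish this without any calculation.

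The size rests on the assumed shifts, correlations and mortality association. The likely effect on the primary result is small. An adjusted Aim 3 model could be moved more, but those outcomes are secondary and their planned unadjusted analysis is sound.

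**What to change.** **(a) Protocol 11.6.i.** For any women not yet enrolled, complete the enrolment questionnaire before the program displays the allocation. This may come too late: SAP section 6 and Table 6.1 place the final DSMB meeting before the 2023 changes, and the 31 January 2023 entry already cites participants' education data. Part (b) is then the usable change.

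**(b) SAP 5.2 and 5.3.** State whether the three scores, parenting confidence included, were recorded before or after the arm was known, and apply one rule to the whole trial.
- *If after, as Protocol 11.6.i reads:* exclude the three scores from the SAP 5.2 adjustment trigger in every model. Keep the unadjusted two-visit GEE as the main Aim 3 result, with the adjusted estimate as a sensitivity analysis only.
- *If all were recorded before, and the rule is fixed before outcomes by arm are seen:* add the enrolment score as a covariate in items 10 to 12 whatever the baseline test shows, with the 2- and 6-week values as the only outcome rows.

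**(c) SAP 5.2.** Say which models the primary analysis covers, and log the change with its date in Table 6.1.

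**Cost.** A few sentences of SAP text, one covariate or one extra estimate per Aim 3 model, and, if still possible, a changed order within the enrolment visit. The downside is that, if the scores were post-allocation, the 11% to 48% variance reduction for the continuous scores is given up in the main result.
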